9.5.3 Safety variables

Adverse events

Treatment-emergent AEs (TEAEs, adverse events that started after the first dose of study treatment or events present prior to the first dose of study treatment but increased in severity based on preferred term) will be summarized up to 12 weeks (84 days) after the last dose. Non-treatment-emergent AEs will be listed in a listing but not summarized.

TEAEs will be summarized by presenting, for each treatment group, the number and percentage of subjects having any AE, having an AE in each primary system organ class and having each individual AE (preferred term). Summaries will also be presented for AEs by severity and for study treatment related AEs. If a subject reported more than one AE with the same preferred term, the AE with the greatest severity will be presented. If a subject reported more than one AE within the same primary system organ class, the subject will be counted only once with the greatest severity at the system organ class level, where applicable. SAEs will also be summarized.

As appropriate, the incidence of AEs will be presented per 100 subject-years of exposure.

Separate summaries will be provided for death, SAE, other TEAEs leading to study treatment interruption or study treatment discontinuation.

A graphical display of relative frequencies within system organ classes and relative risks, as appropriate, will be presented.

When adjudication is required of major cardiovascular events, a summary of those types of events as reported by the investigator and confirmed by adjudication will be provided.

Laboratory data

The summary of laboratory evaluations will be presented for three groups of laboratory tests (hematology, serum chemistry and urinalysis). Descriptive summary statistics for the change from baseline to each study visit will be presented. These descriptive summaries will be presented by test group, laboratory test and treatment group. Change from baseline will only be summarized for subjects with both baseline and post-baseline.

For each parameter, the maximum change from baseline within each study period will be evaluated analogously.

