2.5 Treatments (study treatment, rescue medication, concomitant therapies, compliance)

2.5.1 Study treatment / compliance

The analysis of study treatment data will be based on the safety set. The duration of exposure to study treatment will also be summarized by treatment group. In addition, the number and percentage of subjects with cumulative exposure levels (e.g. any exposure, ≥ 1 week, ≥ 2 weeks, ≥ 3 weeks, ≥ 4 weeks, ≥ 8 weeks, etc.) will be presented.

Duration of exposure of a treatment will be defined as the time from first dose of the treatment to the minimum of (last dose of the treatment + 84 days) and (last visit date).

Duration of exposure (years) = duration of exposure (days) / 365.25

Duration of exposure (100 subject years) = duration of exposure (years) / 100

The analyses of duration of exposure described above will be done for the entire study treatment period.

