2.9.1 Adverse events (AEs)

The crude incidence of treatment emergent adverse events (TEAEs) (i.e. events started after the first dose of study treatment or events present prior to the first dose of study treatment but increased in severity based on preferred term and on or before last dose + 84 days) will be summarized by primary system organ class and preferred term. Confidence intervals for the crude rate will be derived as described in [Section 5.2.4.1](#). Graphical displays of the crude incidence rates will be presented for all AEs and serious AEs by system organ class.

Adverse events reported will be presented first by alphabetical order of system organ class and then in descending frequency according to its incidence in secukinumab group starting from the most common event. For ties in incidence rate of secukinumab group, sort adverse events by incidence rate of adalimumab group. Summaries (crude incidences only) will also be presented for AEs by severity and for study treatment related AEs. If a particular AE 'severity' is missing, this variable will be listed as missing and treated as missing in summaries. If a subject reported more than one adverse event with the same preferred term, the adverse event with the greatest severity will be presented. If a subject reported more than one adverse event within the same primary system organ class, the subject will be counted only once with the greatest severity at the system organ class level, where applicable.

Separate summaries will be provided for adverse events suspected to be related to study drug, deaths, serious adverse events, and adverse events leading to discontinuation and adverse events leading to temporary dose interruption.

Adverse events will also be reported separately by SMQ according to MedDRA. The MedDRA version used for reporting the study will be described in a footnote.

Non-treatment emergent adverse events will be listed.

Algorithms for date imputations will be provided in RAP Programming Dataset Specification (PDS).

For serious adverse events (SAEs) occurred during screening a listing will be prepared for all subjects screened including screening failures.

When adjudication is required of major cardiovascular events, a listing of those types of events as reported by the investigator and confirmed by adjudication will be provided.

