The safety analyses that will be performed for treatment emergent AEs and on treatment labs, ECG and vital signs for the analysis period is described in [Table 2-1](#).

Table 2-1 Overview of analyses on some safety endpoints

Analysis period	AEs & SAEs	AEs by severity	Study-drug related AEs	Risk	Notables for (vitals/ECG), lab criteria
Entire treatment	Cruide incidence	Cruide incidence	Cruide incidence	Cruide incidence	Cruide incidence

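### The protocol foresees adverse event rates per 100 subject-years, as appropriate, but the visible SAP specifies only crude incidence, which may not be comparable if time on treatment differs between arms

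*Protocol*

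**What the plan says.** Protocol 9.5.3 makes the basic adverse event summary a count and percentage, "the number and percentage of subjects having any AE", with the same by system organ class and preferred term. It then adds that, as appropriate, "the incidence of AEs will be presented per 100 subject-years of exposure".

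SAP 2.5.1 defines exposure as running from first dose to the earlier of last dose + 84 days and the last visit, and converts it: "Duration of exposure (100 subject years) = duration of exposure (years) / 100". SAP 2.9.1 summarises treatment-emergent events by crude incidence and adds: "Summaries (crude incidences only) will also be presented for AEs by severity and for study treatment related AEs". The overview table, "Table 2-1 Overview of analyses on some safety endpoints", has five columns (AEs and SAEs, AEs by severity, study-drug related AEs, risk, and notable values). Every cell reads "Cruide incidence" (spelling as in the SAP). The visible parts of SAP 6.2.3 give methods for crude incidence with its confidence interval and for an odds ratio.

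SAP Section 4 states that every protocol analysis for the study report is detailed in the SAP, and lists no change.

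**The concern.** The SAP prepares the denominator for a rate and then, in the text that can be read, never uses it for an adverse event. It does not say that the rate was judged inappropriate.

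This matters because the counting window depends on when treatment stops. A patient whose last dose is at Week 24 is counted for 36 weeks; one who completes dosing at Week 50 is counted for 62 weeks, even if both attend every visit. Protocol 5.5.9 ties stopping both to lack of improvement and to adverse events, and the trial is powered on a difference in response (62% v 50%), so unequal stopping is plausible. Comparative safety is a stated secondary objective. If time on treatment differs, the two percentages in a crude table refer to different average observation times.

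**Working it through.** The documents give no adverse event rate and no discontinuation rate by arm, so there is no figure of the plan to reproduce. The text comparison above carries the point; the arithmetic only sizes it.

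**Inputs from the documents.** The last dosing visit is Week 50 (SAP 2.6.1); by Protocol Table 5-1 the secukinumab arm receives a placebo injection then, so Week 50 is used for both arms. The counting window runs 12 weeks past the last dose.
- Full window: T = (50 + 12) × 7 / 365.25 = 1.188 years.

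**Assumed inputs.** True first-event hazard λ = 0.10 per year in both arms. Discontinuation d = 10% in arm A and 15% or 25% in arm B, with last dose at Week 24 and unrelated to adverse events.
- Short window: t = (24 + 12) × 7 / 365.25 = 0.690 years.

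**Crude incidence** = (1 − d)(1 − e^(−λT)) + d(1 − e^(−λt)), with 1 − e^(−0.1188) = 0.1120 and 1 − e^(−0.0690) = 0.0667.
- d = 10%: 0.90 × 0.1120 + 0.10 × 0.0667 = 10.75%
- d = 15%: 0.85 × 0.1120 + 0.15 × 0.0667 = 10.52%, lower by 0.23 points
- d = 25%: 0.75 × 0.1120 + 0.25 × 0.0667 = 10.07%, lower by 0.68 points

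Subjects with an event divided by person-time to first event or end of window gives 10.0 per 100 subject-years in every case. A simulation with exponentially distributed stopping times gives the same rounded percentages (10.8% v 10.5% to 10.1%).

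**Wider range.** With last dose between Week 8 and Week 36 and rates of 2 to 200 per 100 subject-years, crude incidence in arm B is lower by 0.03 to 5.6 points (ratio 0.89 to 0.996). The largest gap is for a very common event with early stopping.

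**Does the direction hold?** Take 10% v 25% and λ = 0.10. Let a share k of arm B's extra 15% stop because of an event that is counted. Arm B is then 0.75 × 0.1120 + 0.10 × 0.0667 + 0.15 × [k + (1 − k) × 0.0667].
- k = 5%: 10.8%, level with arm A
- k = 20%: 12.9% v 10.8%, so arm B looks worse

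**Does the rate always do better?** Let all events fall in the first 4 weeks (Week 2 on average, 0.038 years) with 10% risk in each arm. Crude incidence is 10% in both. Mean windows are 1.138 and 1.064 years.
- Arm A: 0.10 / (0.90 × 1.138 + 0.10 × 0.038) = 9.7 per 100 subject-years
- Arm B: 0.10 / (0.90 × 1.064 + 0.10 × 0.038) = 10.4 per 100 subject-years

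Here the rate is the misleading measure.

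**The case against.** A reader might infer that the SAP drops a firm protocol commitment without declaring it. The documents do not support that. The protocol line is conditional and supplements percentages, which the SAP does implement. What stands is narrower: the SAP is where the condition should be settled, and it neither specifies the rate nor says why not.

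A reader might also infer that crude incidence makes the arm with more early discontinuation look safer. That needs unequal discontinuation, a hazard that persists over the year, and stopping unrelated to adverse events. The documents establish none of these. Adverse events are themselves grounds for stopping, and the check shows that a small share of such stopping removes or reverses the effect.

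Absence cannot be fully proved from this text. SAP numbering has gaps, 2.9.1 cites a Section 5.2.4.1 that is not visible, Table 2-1 covers only some endpoints, and the reference list holds sources on Poisson confidence limits that no visible section uses. A rate method may sit in removed text. Table 2-1 is readable, however, and its AE and SAE cell gives crude incidence alone.

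Finally, the effect is small against sampling error. With 425 per arm and incidence near 10.5%, the 95% half-width for a difference is 1.96 × √(2 × 0.105 × 0.895 / 425) = 4.1 points. Safety carries no hypothesis in the testing strategy, and the SAP already tabulates exposure and discontinuation reasons by arm, so an imbalance would be visible. This limits the importance of the point but does not remove it.

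**Conclusion.** The point holds in a limited form. The visible SAP specifies crude incidence for adverse events, leaves a 100-subject-year unit unused, and does not settle the protocol's conditional provision. Crude incidence may not be comparable between arms if time on treatment differs. Under equal constant hazards of 10 per 100 subject-years, assumed discontinuation of 10% v 15% to 25% with last dose at Week 24, and stopping unrelated to adverse events, the gap is 0.2 to 0.7 points. Other assumptions change its size, and the reasons for stopping can change its sign. Neither measure is reliable alone, which is the case for showing both. This is a worthwhile improvement to safety reporting; it does not affect the efficacy conclusions.

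**What to change.** In SAP 2.9.1 and Table 2-1, add first-event incidence per 100 subject-years with a 95% CI beside crude incidence, at least for any AE, SAEs and the risk events, and give the interval method in 6.2.3. End each patient's person-time at the earliest of first event, last dose + 84 days and last visit date. The last-visit limit is already in SAP 2.5.1; without it, patients who leave early would be credited with unobserved time. If the rate is judged inappropriate, record that and the reason in SAP Section 4.

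The cost is modest. SAP 2.5.1 gives total exposure, so person-time to first event must be derived separately for each term reported. The rate assumes a roughly constant hazard and can mislead for events clustered early, so crude incidence must stay alongside. Alpha, sample size and trial conduct are unaffected.

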9.6 Interim analyses

The primary analysis may be conducted when all patients complete the Week 52 visit. In the case this analysis is conducted, all patients will have final data pertaining to the Week 52 endpoints, thus no adjustment to the type I error will be made and the final analysis after the last visit (Week 68) will include the data collected from the post-treatment follow-up period.

9.7 Sample size calculation

A family-wise error will be set to two-sided α =0.05 to control for type I error. The primary objective of secukinumab 300 mg versus adalimumab with respect to ACR20 response at Week 52 will be tested at a two sided 0.05 alpha level.

An ACR20 response rate of about 50% for the TNF α inhibitor naïve without MTX use (monotherapy) population at week 48 was reported in Humira study (Gladman 2007). The response on secukinumab 300 mg is estimated to be 62% in the TNF α inhibitor naïve monotherapy population based on the lower bound of 80% confidence interval of Meta-analysis results of the study FUTURE-2 (McInnes 2015) and unpublished study FUTURE-3. With 425 subjects per treatment group there would be approximately 94% power to detect a treatment difference of 12% at a two-sided 0.05 alpha level in ACR20 response rates (Chi Square test, NQuery 7.0) between secukinumab 300 mg and adalimumab in the evaluation of the primary efficacy hypothesis at Week 52. The overall sample size will be 850 patient for a randomization ratio of 1:1 (secukinumab 300 mg 425 patients, and adalimumab 425 patient). The estimated

power with the chosen sample size for other efficacy endpoints based on the data available for adalimumab and meta-analysis results of the study FUTURE-2 and study FUTURE-3 are summarized in Table 9-2. The assumptions for power calculation in Table 9-2 are presented in Table 9-1.

Table 9-1 Assumption for sample size and power calculation

Endpoint	Secukinumab 300mg expected values	Adalimumab (N=76) observed values
ACR20	62%	50%
PASI90	63%	38% (N=40)
ACR50	49%	38%
HAQ-DI change*	-0.59 (0.5)	-0.4 (0.5)(N=61)
Resolution of enthesitis	61%	33%

^{*}mean (standard deviation)

Sources: The value for Secukinumab is from the lower bound of 80% confidence interval of a meta-analysis based on FUTURE-2 and unpublished results from FUTURE-3 data, the values for other endpoints for Secukinumab are from the means of the same meta-analysis, the values for Adalimumab are from Humira® study (Gladman 2007).

Based on Table 9-1, power calculation for superiority tests of different endpoints are presented below in Table 9-2.

Table 9-2 Power for superiority tests for primary and secondary endpoints (two-sided, α =0.05)

Endpoint	Power*
ACR20 (H1)	94%
PASI90 (H2)	99%
ACR50 (H3)	91%
HAQ-DI (H4)	99%
Resolution of enthesitis (H5)	99%

^{*} power does not consider dependence of the endpoints in the Testing Strategy, power for PASI90 and enthesitis is based on the assumption that a subset of half of the population (213 subjects per group) has data of these two endpoints.

10 Ethical considerations

10.1 Regulatory and ethical compliance

This clinical study was designed and shall be implemented, executed and reported in accordance with the ICH Harmonized Tripartite Guidelines for Good Clinical Practice, with applicable

local regulations (including European Directive 2001/20/EC, US CFR 21, and Japanese Ministry of Health, Labor, and Welfare), and with the ethical principles laid down in the Declaration of Helsinki.

10.2 Informed consent procedures

Eligible subjects may only be included in the study after providing IRB/IEC-approved informed consent (witnessed, where required by law or regulation), or, if incapable of doing so, after such consent has been provided by a legally acceptable representative(s) of the subject. In cases where the subject's representative gives consent, the subject should be informed about the study to the extent possible given his/her understanding. If the subject is capable of doing so, he/she must indicate assent by personally signing and dating the informed consent document or a separate assent form. Informed consent must be obtained before conducting any study-specific procedures (e.g. all of the procedures described in the protocol). The process of obtaining informed consent must be documented in the patient source documents.

Novartis will provide to investigators in a separate document a proposed informed consent form that complies with the ICH GCP guideline and regulatory requirements and is considered appropriate for this study. Any changes to the proposed consent form suggested by the investigator must be agreed to by Novartis before submission to the IRB/IEC, and a copy of the approved version must be provided to the Novartis monitor after IRB/IEC approval.

Women of child bearing potential must be informed that taking the study treatment may involve unknown risks to the fetus if pregnancy were to occur during the study and agree that in order to participate in the study they must adhere to the contraception requirement for the duration of the study, and for a minimum 16 weeks or longer if local label requires it (e.g. 20 weeks for secukinumab, 5 months for adalimumab in EU) after the last dose. If there is any question that the subject will not reliably comply, they should not be entered in the study.

The study includes an optional PG ICF which requires a separate signature if the subject agrees to participate. It is required as part of this protocol that the Investigator presents this option to the subject. The process for obtaining consent should be exactly the same as described above for the main informed consent.

Declining to participate in these PG assessments will in no way affect the patient's ability to participate in the main research study.

In the event that Novartis wants to perform testing on the samples that are not described in this protocol, additional IRB and/or IEC approval will be obtained.

10.3 Responsibilities of the investigator and IRB/IEC

Before initiating a trial, the investigator/institution must obtain approval/favorable opinion from the IRB/IEC for the trial protocol, informed consent form, consent form updates, subject recruitment procedures (e.g., advertisements) and any other written information to be provided to subjects. Prior to study start, the investigator is required to sign a protocol signature page confirming his/her agreement to conduct the study in accordance with these documents and all of the instructions and procedures found in this protocol and to give access to all relevant data and records to Novartis monitors, auditors, Novartis Quality Assurance representatives, designated agents of Novartis, IRBs/IECs, and regulatory authorities as required. If an

inspection of the clinical site is requested by a regulatory authority, the investigator must inform Novartis immediately that this request has been made.

10.4 Publication of study protocol and results

Novartis assures that the key design elements of this protocol will be posted in a publicly accessible database such as clinicaltrials.gov. In addition, upon study completion and finalization of the study report the results of this trial will be either submitted for publication and/or posted in a publicly accessible database of clinical trial results.

11 Protocol adherence

This protocol defines the study objectives, the study procedures and the data to be collected on study participants. Additional assessments required to ensure safety of subjects should be administered as deemed necessary on a case by case basis. Under no circumstances is an investigator allowed to collect additional data or conduct any additional procedures for any research related purpose involving any investigational drugs.

Investigators ascertain they will apply due diligence to avoid protocol deviations. If an investigator feels a protocol deviation would improve the conduct of the study this must be considered a protocol amendment, and unless such an amendment is agreed upon by Novartis and approved by the IRB/IEC, it cannot be implemented. All significant protocol deviations will be recorded and reported in the CSR.

A personal history of psoriasis is defined as a history of psoriasis that may be obtained from a patient, family physician, dermatologist, rheumatologist, or other qualified health care provider. (1 points)

A family history of psoriasis is defined as a history of psoriasis in a first- or second- degree relative according to patient report. (1 points)

Typical psoriatic nail dystrophy including onycholysis, pitting, and hyperkeratosis observed on current physical examination (1 point)

A negative test result for the presence of rheumatoid factor by any method except latex (1 point)

Either current dactylitis, defined as swelling of an entire digit, or a history of dactylitis recorded by a rheumatologist (1 point)

Radiographic evidence of juxta-articular new bone formation appearing as ill-defined ossification near joint margins (but excluding osteophyte formation) on plain radiographs of the hand or foot (1 point)

Total score:

(The CASPAR criteria eCRF will autopopulate the total number of points of the CASPAR criteria met by the subject. If the total score ≥ 3 , the subject meets CASPAR criteria for PsA diagnosis.)

* Current psoriasis is assigned a score of 2; all other features are assigned a score of 1

14 Appendix 2: Guidelines for administering the questionnaires for patient reported outcomes

Before trial start

Study coordinators should familiarize themselves with the PRO questionnaire(s) in the trial and identify any items where a patient's response might highlight issues of potential concern.

Before completion

Subjects should be provided with the correct questionnaire at the appropriate visits and in the appropriate language

Subjects should have adequate space and time to complete the forms

Patients should be provided with a firm writing surface (such as a table or a clip board)

Questionnaire should be administered before the clinical examination

During completion

Administrator may clarify the questions but should not influence the response

Only one response for each question

Also see "Addressing Problems and Concerns"

After completion

Check for completeness and not for content*

Data should be sent from the eCRF / electronic device

Data should be reviewed by Investigator for AEs

*However, any response which may directly impact or reflect the patient's medical condition (e.g. noting of depression) should be communicated by the study coordinator to the investigator).

Addressing Problems and Concerns

Occasionally a patient may have concerns or questions about the questionnaires administered. Guidance related to some of the most common concerns and questions are given below.

The patient does not want to complete the questionnaire(s)

Tell the patient that completion of the questionnaire(s) is voluntary. The goal is to better understand the physical, mental and social health problems of patients. Emphasize that such information is as important as any other medical information and that the questionnaire(s) is simple to complete. Suggest that the questionnaire(s) may be different from anything the respondent has filled in the past. If the patient still declines, retrieve the questionnaires. Record the reason for the decline and thank the patient.

The patient is too ill or weak to complete the questionnaire(s)

In these instances, the coordinator may obtain patient responses by reading out loud each question, followed by the corresponding response categories, and entering the patient's response. No help should be provided to the patient by any person other than the designated study coordinator. The coordinator should not influence patient responses. The study coordinator cannot translate the question into simpler language and has to be read verbatim.

The patient wants someone else to complete the questionnaire(s)

In no case should the coordinator or anyone other than the patient provide responses to the questions. Unless specified in the study protocol, proxy data are *not* an acceptable substitute for patient self-report. Patients should be discouraged from asking a family member or friend for help in completing a questionnaire.

The patient does not want to finish completing the questionnaire(s)

If non-completion is a result of the patient having trouble understanding particular items, ask the patient to explain the difficulty. Re-read the question for them *verbatim* but do not rephrase the question. If the respondent is still unable to complete the questionnaire, accept it as incomplete. Thank the patient.

The patient is concerned that someone will look at his/her responses

Emphasize that all responses are to be kept confidential. Point out that their names do not appear anywhere on the questionnaire, so that their results will be linked with an ID number and not their name. Tell the patient that his/her answers will be pooled with other patients' answers and that they will be analyzed as a group rather than as individuals. Tell the patient that completed forms are not routinely shared with treating staff and that their responses will only be seen by you (to check for completeness) and by the investigator. Any response which may directly impact on or reflect their medical condition (*e.g.* noting of severe depression) will be communicated by the coordinator to the physician.

The patient asks the meaning of a question/item

While completing the questionnaire, some patients might ask the meaning of specific items so that they can better understand and respond. If this happens, assist the patient by rereading the question for them *verbatim*. If the patient asks to interpret the meaning of an item, do not try to explain it, but suggest that he/she use his/her own interpretation of the question. Patients should answer the questions based on what *they* think the questions mean.

A General Information about all questionnaire(s):

All questionnaires have to be completed by the patients in their local languages using an electronic device. The questionnaires should be completed by the patients in a quiet area free from disturbance, and before any visit assessments. Patients should receive no help from family members; if questions cannot be answered alone (due to problems with reading or understanding), then the doctor or nurse should read the questions and record the patient's responses without influencing their answers. The information provided is strictly confidential and will be treated as such. If a patient has missed a question or given more than one response

per question, then this should be brought to patient. Incomplete questions should not be accepted without first encouraging the patient to complete unanswered questions.

The investigator must complete the patient/visit information on the electronic device and ensure that the center number, patient's number and initials are identical to the CRF. As there are no source data for this questionnaire, the data queries will be restricted to patient/visit information.

15 Appendix 3: American College of Rheumatology (ACR) Measures and Criteria of Response

Number of tender joints

Seventy-eight joints (78) are scored as either tender or not tender: 8 distal interphalangeal, 10 proximal interphalangeal, 10 metacarpophalangeal and 2 first carpometacarpal joints of the hands, 8 distal interphalangeal, the 10 metatarsophalangeal and 10 proximal interphalangeal joints of the feet, the 2 wrists, 2 elbows, 2 shoulders, 2 acromioclavicular, 2 sternoclavicular, 2 temporomandibular, 2 hips, 2 knees, 2 talo-tibial, and 2 mid-tarsal joints.

Joint tenderness is to be scored present (1) or absent (0).

Number of swollen joints

Joints are to be scored as either swollen (1) or not swollen (0). The 76 joints to be examined for swelling are the same as those examined for tenderness, however excluding both hip joints.

Patient's assessment of PsA pain

On a 100 mm non-anchored visual analog scale, from no pain to unbearable pain.

Patient's global assessment of disease activity

On a 100 mm non-anchored visual analog scale, from no arthritis activity to maximal arthritis activity, after the question "Considering all the ways your arthritis affects you, draw a line on the scale for how well you are doing".

Physician's global assessment of disease activity

On a 100 mm non-anchored visual analog scale, from no arthritis activity to maximal arthritis activity.

Patient's assessment of physical function

Health Assessment Questionnaire – HAQ-DI[©]ACR20/50/

A patient will be considered as improved according the ACR20 criteria* if she/he has at least 20% improvement in

- the two following measures:
 - Tender joint count
 - Swollen joint count
- and at least 3 of the following 5 measures:
 - Patient's assessment of pain
 - Patient's global assessment of disease activity
 - Physician's global assessment of disease activity
 - Health Assessment Questionnaire (HAQ[©]) score
 - C-reactive protein (CRP)/Erythrocyte Sedimentation Rate (ESR).

ACR50 = 50% improvement in at least 3 of the 5 measures and 50% improvement in the swollen and tender joint count.

Reference: (Felson 1995)

17 Appendix 5: The Psoriasis Area and Severity Index (PASI)

The PASI is a system used for assessing and grading the severity of psoriatic lesions and their response to therapy. The PASI produces a numeric score that can range from 0 to 72. The severity of disease is calculated as follows. In the PASI system, the body is divided into 4 regions: the head (h), trunk (t), upper extremities (u), and lower extremities (l), which account for 10%, 30%, 20% and 40% of the total BSA, respectively. Each of these areas is assessed separately for erythema, induration and desquamation (scaling), which are each rated on a scale of 0 to 4. The scoring system for the signs of the disease (erythema, induration, and desquamation (scaling)) are:

0 = none; 1 = slight; 2 = moderate; 3 = severe; and 4 = very severe.

The scale for estimating the area of involvement for psoriatic lesions is outlined below.

0 = no involvement

1 = 1% to 9% involvement

2 = 10% to 29% involvement

3 = 30% to 49% involvement

4 = 50% to 69% involvement

5 = 70% to 89% involvement

6 = 90% to 100% involvement

To help with the area assessments, the following conventions should be noted:

- the neck is considered part of the head
- the axillae and groin are part of the trunk
- the buttocks are part of the lower extremities

The PASI formula is: PASI = 0.1 (Eh + Ih + Dh) Ah + 0.3 (Et +It+ Dt) At+ 0.2 (Eu + Iu + Du) Au+ 0.4 (El +II+ Dl) AI (where E= erythema, I = induration, D = desquamation and A = area)

Table 17-1 PASI Scoring Worksheet

	Head	Upper extremities	Trunk	Lower extremities
Redness †				
Thickness †				
Scale †				
Sum of rows 1, 2, and 3				
Area score ‡				
Score of row 4 x row 5 x the area multiplier	Row 4 x row 5 x 0.1	Row 4 x row 5 x 0.2	Row 4 x row 5 x 0.3	Row 4 x row 5 x 0.4
Sum row 6 for each column for PASI score				

- a. Divide body into four areas: head, arms, trunk to groin, and legs to top of buttocks.
- b. Generate an average score for the erythema, thickness, and scale for each of the 4 areas (0=clear, 1-4=increasing severity).
- c. Sum scores of erythema, thickness, and scale for each of the 4 area.
- d. Generate a percentage for skin covered with psoriasis for each area and convert that to a 0-6 scale. ‡
- e. Multiply score of item c above times item d above for each area and multiply that by 0.1, 0.2, 0.3 and 0.4 for head, arms, trunk, and legs, respectively.
- f. Add these scores to get the PASI score.
- † Erythema, thickness, and scale are measured on a 0-4 scale (none, slight, mild, moderate, severe)
- ‡ Area scoring criteria (score: % involvement).
 - 0: 0% (clear)
 - 1: <10%
 - 2: 10-<30%
 - 3: 30-<50%
 - 4: 50-<70%
 - 5: 70-<90%
 - 6: 90-100%

Derived from Feldman SR, Krueger GG (2005). Psoriasis assessment tool in clinical trials. Ann Rheum Dis; 64 (Suppl 2);ii65-8, ii69-73.

18 Appendix 6: Liver event and laboratory trigger definitions and follow-up requirements

Table 18-1 Liver Event and Laboratory Trigger Definitions

	Definition/ threshold
LIVER	$3 \times ULN < ALT / AST \le 5 \times ULN$
LABORATORY TRIGGERS	$1.5 \times ULN < TBL \le 2 \times ULN$
LIVER EVENTS	ALT or AST $> 5 \times ULN$
	$ALP > 2 \times ULN$ (in the absence of known bone pathology)
	TBL $> 2 \times ULN$ (in the absence of known Gilbert syndrome)
	ALT or AST $> 3 \times ULN$ and INR > 1.5
	Potential Hy's Law cases (defined as ALT or AST $> 3 \times$ ULN and TBL $> 2 \times$ ULN [mainly conjugated fraction] without notable increase in ALP to $> 2 \times$ ULN)
	Any clinical event of jaundice (or equivalent term)
	ALT or AST $>$ 3 \times ULN accompanied by (general) malaise, fatigue, abdominal pain, nausea, or vomiting, or rash with eosinophilia
	Any adverse event potentially indicative of a liver toxicity *

^{*} These events cover the following: hepatic failure, fibrosis and cirrhosis, and other liver damage-related conditions; non-infectious hepatitis; benign, malignant and unspecified liver neoplasms

TBL: total bilirubin; ULN: upper limit of normal

Table 18-2 Follow up Requirements for Liver Events and Laboratory Triggers

Criteria	Actions required	Follow-up monitoring	
Potential Hy's Law case ^a	Discontinue the study drug immediately	ALT, AST, TBL, Alb, PT/INR, ALP	
	Hospitalize, if clinically appropriate	and γGT until resolution ^c (frequency at investigator discretion)	
	Establish causality		
	Complete liver eCRF		
ALT or AST			
$> 8 \times ULN$	Discontinue the study drug immediately	ALT, AST, TBL, Alb, PT/INR, ALP	
	Hospitalize if clinically appropriate	and γGT until resolution ^c (frequency at investigator discretion)	
	Establish causality	,	
	Complete liver eCRF		
> 3 × ULN and INR > 1.5	Discontinue the study drug immediately	ALT, AST, TBL, Alb, PT/INR, ALP and γGT until resolution ^c (frequency at investigator discretion)	
	Hospitalize, if clinically appropriate		
	Establish causality		

Criteria	Actions required	Follow-up monitoring	
	Complete liver eCRF		
> 5 to $\le 8 \times ULN$	Repeat LFT within 48 hours	ALT, AST, TBL, Alb, PT/INR, ALP and γGT until resolution ^c (frequency at investigator discretion)	
	If elevation persists, continue follow- up monitoring		
	If elevation persists for more than 2 weeks, discontinue the study drug		
	Establish causality		
	Complete liver eCRF		
$> 3 \times ULN$	Discontinue the study drug immediately	ALT, AST, TBL, Alb, PT/INR, ALP	
accompanied by symptoms ^b	Hospitalize if clinically appropriate	and γGT until resolution ^c (frequency at investigator discretion)	
2) ::: ,	Establish causality		
	Complete liver eCRF		
$>$ 3 to \leq 5 \times ULN	Repeat LFT within the next week	Investigator discretion	
(patient is asymptomatic)	If elevation is confirmed, initiate close observation of the patient	Monitor LFT within 1 to 4 weeks	
ALP (isolated)			
$> 2 \times ULN$ (in the	Repeat LFT within 48 hours	Investigator discretion	
absence of known bone pathology)	If elevation persists, establish causality	Monitor LFT within 1 to 4 weeks or at next visit	
	Complete liver eCRF		
TBL (isolated)			
$> 2 \times ULN$ (in the	Repeat LFT within 48 hours	ALT, AST, TBL, Alb, PT/INR, ALP	
absence of known Gilbert syndrome)	If elevation persists, discontinue the study drug immediately	and γGT until resolution ^c (frequency at investigator discretion)	
	Hospitalize if clinically appropriate	Test for hemolysis (e.g., reticulocytes, haptoglobin,	
	Establish causality	unconjugated [indirect] bilirubin)	
	Complete liver eCRF		
> 1.5 to ≤ 2 × ULN	Repeat LFT within the next week	Investigator discretion	
	If elevation is confirmed, initiate	Monitor LFT within 1 to 4 weeks	
(patient is asymptomatic)	close observation of the patient	or at next visit	
Jaundice	Discontinue the study drug immediately	ALT, AST, TBL, Alb, PT/INR, ALP	
	Hospitalize the patient	and γGT until resolution ^c (frequence at investigator discretion)	

Criteria	Actions required	Follow-up monitoring
	Establish causality	
	Complete liver eCRF	
Any AE potentially indicative of a liver toxicity*	Consider study drug interruption or discontinuation	Investigator discretion
	Hospitalization if clinically appropriate	
	Establish causality	
	Complete liver eCRF	

^{*} These events cover the following: hepatic failure, fibrosis and cirrhosis, and other liver damage-related conditions; non-infectious hepatitis; benign, malignant and unspecified liver neoplasms

TBL: total bilirubin; ULN: upper limit of normal

 $[^]a$ Elevated ALT/AST > 3 \times ULN and TBL > 2 \times ULN but without notable increase in ALP to > 2 \times ULN

^b (General) malaise, fatigue, abdominal pain, nausea, or vomiting, or rash with eosinophilia

^c Resolution is defined as an outcome of one of the following: (1) return to baseline values, (2) stable values at three subsequent monitoring visits at least 2 weeks apart, (3) remain at elevated level after a maximum of 6 months, (4) liver transplantation, and (5) death.

19 **Appendix 7: Clinically notable laboratory values**

The following guidance will be used to define expanded limits and notable abnormalities of key laboratory outcomes.

Page 106

Clinically notable values will be forwarded to Novartis in the same time as sent to the investigators. Any intervention based on these laboratory values should be discussed with Novartis personnel.

Table 19-1 Clinically notable laboratory values

Laboratory variable	Notable criteria	
Liver function and related variables		
SGOT (AST)	>3 x ULN	
SGPT (ALT)	>3 x ULN	
Bilirubin	>2 x ULN	
Alkaline phosphatase	>2.5 x ULN	
Renal function, metabolic and electrolyte variables		
Creatinine (serum)	>2 x ULN	
Hematology variables		
Hemoglobin	20 g/L decrease from Baseline	
Platelet count	<100 x 10 ⁹ /L	
White blood cell count	<0.8 x LLN	
Neutrophils	<0.9 x LLN
